The SARS-CoV-2 spike antibody and T cell assays will all be processed at Montefiore Medical Center laboratories as per Abbott and EUROIMMUN's instructions for use. The SARS-CoV-2 IgG II assay results will be made available in Epic for review by the research team, primary oncologist, and patient when available, however, the T cell assays will be used for research purposes only and documented in an Excel Data Collection Sheet as below. For the neutralization assay, we will be utilizing Genscripts' "SARS-CoV-2 Surrogate Virus Neutralization Test (sVNT) Kit (RUO)" and running the test on stored serum samples. The neutralization assay is also a research assay and the results will be documented in the aforementioned Excel Data Collection Sheet.

The protocol when initially approved (version date July 23 2021) included a safety-run in phase for the 3rd dose of vaccine. So far we enrolled 4 patients into the safety run-in phase that received booster dose before FDA authorization and have not noted safety concerns in these patients. However, given that FDA has authorized a third dose for patients with compromised immune systems, we propose to close the run-in phase early for the mRNA vaccines and move ahead with enrolling patients based on the modified inclusion criteria in line with FDA guidance. Patients that have received the Ad26.CoV2.S vaccine will be offered participation in the study and will have a run-in phase where 3 patients will receive the vaccine first and followed closely with symptom check at 48 hours and 1 week post-vaccination. Once safety of booster mRNA vaccine post adenoviral vaccine is established, further enrollment onto the adenoviral vaccine arm will occur.

After patients consent they will be scheduled to receive a booster dose of the BNT162b2 or mRNA-1273 (Pfizer/BioNTech/Moderna) vaccine at the Montefiore Vaccine Center by an experienced team of vaccinators. Each patient will be observed for a minimum of 15 minutes after their vaccination to monitor for any adverse effects in the Montefiore Vaccine Center as per the Vaccine Center protocol.

Each patient enrolled in the study will also be provided 24-hour contact information to call in case of an emergency or for any other after hour concerns.

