Patients will undergo spike antibody testing at D0 of the study and then return for a study visit four weeks after their booster vaccine to complete a SARS-CoV-2 spike antibody test and T cell response assays to determine virus neutralizing activity. Side effects to the booster dose will be noted via a questionnaire that patients would fill out at this visit which will collect data pertaining to side effects and their severity compared to prior vaccine doses. Patients will return for a final study visit five to six months after their booster vaccine to assess for long-term side effects and to obtain SARS-CoV-2 spike antibody test and T cell response assays in patients who became seropositive after 4 weeks to determine if immunogenicity is sustained.

Follow up tests for cohorts 2 and 3: Patients will undergo spike antibody testing as well as baseline laboratory studies including CBC, lymphocyte subsets, quantitative immunoglobulins, T-cell response and neutralizing activity at enrollment. Patients will then receive their 4th booster vaccine (D0). Patients will return for a study visit at least 28 days after their booster vaccine to complete a SARS-CoV-2 spike antibody

test including follow-up laboratory studies as listed above. Side effects to the booster dose will be noted via a questionnaire that patients would fill out at this visit which will collect data pertaining to side effects and their severity compared to prior vaccine doses. Patients will then return for further study visits at 3 months, 6 months and 12 months and then a final study visit 24 months after their booster vaccine to assess for long-term side effects and to obtain SARS-CoV-2 spike antibody test, T cell response assays, and other laboratory studies as above in patients who became seropositive after 4 weeks to determine if immunogenicity is sustained.

Sample size

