In the prior version of the protocol (version July 23 2021), we had outlined a careful detailed data safety monitoring plan which we have changed in light of the FDA authorization for booster dosing with the BNT162b and mRNA1273 vaccines. For patients that have received one of these mRNA vaccination series who have consented to participate in the study, data for side effects will be collected via a questionnaire that is administered at the 4 week visit.

For patients that have received adenoviral vaccine, we plan for a safety run-in when only 3 subjects from the adenoviral vaccine type will be dosed and monitored for an extended period following dosing as well as monitored closely for one week. Only if no unexpected or severe side effects (such as adverse events leading to emergency room visit, anaphylaxis, hospitalization or death) are noted during this period, will further patients be allowed to be dosed. Weekly study team meetings will be held during the initial study period while vaccinations are being performed and for at least 4 weeks afterwards to review available safety data and alert IRB and DSMC according to institutional protocols if any serious AEs are identified. In addition, our study will be monitored by the Montefiore/Einstein Cancer Center DSMC.

Due to the updated CDC recommendations published on December 16, 2021 regarding use of the Ad26.COV2.S (Johnson & Johnson) vaccine given its rare but persistent serious adverse event thrombosis with thrombocytopenia syndrome (TTS), patients in Cohort 2 will continue to fill out and receive safety questionnaires at each study visit during follow-up to screen for this rare adverse event.

Informed consent

Patients will be scheduled for a consenting visit with a member of the research group listed as consenting provider on the IRB protocol. Study rationale, alternatives, potential risks/benefits, confidentiality issues will be carefully reviewed and voluntary nature of study participation emphasized. Ample time will be provided for questions and the consenting process will be documented. If patients sign the ICF, screening will be initiated, and a copy of the consent will be given to the patient.

Risk/Benefit

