Similarly, the mRNA 1273 vaccine underwent dose finding and safety phase 1 (NCT04283461) and phase 2 (NCT04405076) trials after which in the phase 3 trial of mRNA 1273 vaccine (COVE study), approximately 30,000 participants were recruited in a randomized manner that received 2 doses of 100 μ g 1 month apart. The most common solicited adverse reactions (ARs) after the two-dose series was injection site pain (86.0%). Solicited systemic adverse events occurred more often in the Moderna COVID-19 vaccine group (54.9% and 79.4%) than in the placebo (42.2% and 36.5%) group after both the first dose and the second dose respectively and were most commonly headache, fatigue and myalgia. While the majority of these ARs were mild (grade 1) or moderate (grade 2), there was a higher occurrence of severe (grade 3) reactions in the Moderna COVID-19 Vaccine group after the first (2.9%) and second (15.8%) injections. The majority of local solicited ARs occurred within the first one to two days after injection and generally persisted for a

median of one to two days. Similar to the BNT162b2 vaccine, some reports of myocarditis and pericarditis have been reported post-mRNA 1273 vaccination (see *Full EUA Prescribing Information*¹⁷). A recent randomized controlled trial of three vs two doses of mRNA 1273 vaccine in solid-organ transplant recipients, reported that any local and systemic events were slightly more common after the third dose of mRNA-1273 than after the dose of placebo, but no grade 3 or 4 events and no cases of acute rejection occurred¹⁸.

As to safety of the Ad26.COV2.S vaccine in study COV3001, the most common local solicited adverse reaction ($\geq 10\%$) reported was injection site pain (48.6%). The most common systemic adverse reactions ($\geq 10\%$) were headache (38.9%), fatigue (38.2%), myalgia (33.2%), and nausea (14.2%) (see Tables 1 to 4). Severe allergic reactions, including anaphylaxis, have been reported following administration of the Janssen COVID-19 vaccine.

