Assessment		Screening	Initial visit	Vaccine day (D0)	D28	D150-180
Informed consent	ICF	X	X			
Demographics	Demographics	X				

	Medical history	X				
	COVID vaccine history	X				
	Inclusion/Exclusion Criteria	X				
	SARS-CoV-2 Spike antibody	X				
Safety	Vital signs		X		X	X
	SpO2		X		X	X
	Physical exam		X	X	X	X
	Document Side effects				X	X
	Side Effect Questionnaire				X	
Intervention	Vaccine administration			X		
	Vaccine questionnaire				X	
Outcome	SARS-CoV-2 Spike antibody		X		X	X
	SARS-CoV-2 Neutralization assay		X		X	X
	EUROIMMUN T-cell assay		X		X	X

Study calendar cohort 2

Assessment		Screening	Initial visit	Vaccine day (D0)	D28	D90	D180	D365	D730
Informed consent	ICF	X	X						
Demographics	Demographics	X							
	Medical history	X			X	X	X	X	X
	COVID vaccine history	X			X	X	X	X	X
	Inclusion/Exclusion Criteria	X							
	SARS-CoV-2 Spike antibody	X							
Intervention	Vaccine administration			X					
	Vaccine/safety questionnaire				X	X	X	X	X
Outcome	SARS-CoV-2 Spike antibody		X		X	X	X	X	X
	SARS-CoV-2 Neutralization assay		X		X	X	X	X	X
	EUROIMMUN T-cell assay		X		X	X	X	X	X

For study visits a 7 day window will be allowable for the 4 week follow up visit, a 14 day window will be allowable for the day 90 visit and 28 day window will be allowable for the rest of the study visits.

Study calendar cohort 3

Assessment		Screening	Initial visit	Vaccine day (D0)	D28	D90	D180	D365	D730
Informed consent	ICF	X	X						
Demographics	Demographics	X							
	Medical history	X			X	X	X	X	X
	COVID vaccine history	X			X	X	X	X	X
	Inclusion/Exclusion Criteria	X							
	SARS-CoV-2 Spike antibody	X							
Intervention	Vaccine administration			X					
	Vaccine/safety questionnaire				X	X	X	X	X
Outcome	SARS-CoV-2 Spike antibody		X		X	X	X	X	X
	SARS-CoV-2 Neutralization assay		X		X	X	X	X	X
	EUROIMMUN T-cell assay		X		X	X	X	X	X

For study visits a 7 day window will be allowable for the 4 week follow up visit, a 14 day window will be allowable for the day 90 visit and 28 day window will be allowable for the rest of the study visits.

External Site

Institution	Point of Contact	Role
EUROIMMUN	[name], [contact]	Reagents and supplies, running samples.
International Cancer Covid Vaccination Consortium	Crick Legal [contact]	Data Sharing with ICCV. DUA will be reviewed and executed to account for this activity.

References:

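### Apart from the run-in patients, side effects are first recorded by recall at about day 28 in every cohort, so the secondary safety outcome carries avoidable recall error for mild and moderate reactions

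*Combined protocol and SAP*

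**What the plan says.** The combined protocol and SAP lists safety of the booster as a secondary outcome under each of cohorts 1, 2 and 3, and side effects appear among the aims of each.

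On collection, the Data and Safety Monitoring Plan states, for patients who had an mRNA series, that "data for side effects will be collected via a questionnaire that is administered at the 4 week visit". The Methods, describing the four-week visit, say: "Side effects to the booster dose will be noted via a questionnaire that patients would fill out at this visit". The same sentence is repeated for cohorts 2 and 3, where the visit is described thus: "Patients will return for a study visit at least 28 days after their booster vaccine". The form is to gather "data pertaining to side effects and their severity compared to prior vaccine doses".

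The calendars agree. In cohort 1 the row "Side Effect Questionnaire" is marked only at D28, and side effects are documented at D28 and at the last visit. In cohorts 2 and 3 the vaccine/safety questionnaire is first marked at D28. None of the calendars has a visit between the vaccine day and D28. The notes under the cohort 2 and 3 calendars add that "a 7 day window will be allowable for the 4 week follow up visit", without saying whether it runs in both directions.

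There is one stated exception. The first three patients previously given the adenoviral vaccine are "followed closely with symptom check at 48 hours and 1 week post-vaccination".

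On the time course of reactions, the Risk/Benefit section says of the mRNA-1273 phase 3 trial: "The majority of local solicited ARs occurred within the first one to two days after injection and generally persisted for a". The sentence then ends by giving the median duration as 1 to 2 days.

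**The concern.** Short-lived reactions such as a sore arm or a day of fatigue are the bulk of what a booster safety questionnaire picks up. If patients are first asked about them weeks after they have ended, some will be forgotten and some will be misgraded. In patients on active cancer treatment, some symptoms will also be hard to date to the vaccine rather than to therapy. Asking for severity relative to earlier doses adds recall of still older events.

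What is at stake is the descriptive safety result for mild and moderate reactions. In cohorts 1 and 3 the recorded rates may be off by an unknown amount. In cohort 2 the documents describe randomization but no blinding. If patients know which vaccine they received, what they remember could depend on it, and a side-by-side table of the arms would then mix true differences with differences in recall.

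**Working it through.** The plan gives no figure for this point, so there is nothing to reproduce. The check has three parts.

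**1. Is there any earlier structured collection?**

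- Vaccine day: every patient is observed for at least 15 minutes (Methods; safety monitoring text for cohorts 2 and 3). This catches immediate events only.
- Between D0 and D28: a 24-hour contact number (Methods) and weekly team meetings that review whatever safety data are available (Data and Safety Monitoring Plan). Both depend on spontaneous reports.
- Run-in: 3 adenoviral-primed patients have checks at 48 hours and 1 week. Another 4 patients were enrolled in the closed mRNA run-in; the current text does not give their monitoring schedule.
- D28: the first scheduled questionnaire in all three calendars.

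Share of planned patients with an earlier scheduled check:

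- Planned total (upper limits in Sample size): 250 + 100 + 80 = 430.
- Current run-in only: 3/430 = 0.7%; within cohort 1, 3/250 = 1.2%.
- Counting the closed run-in as well: at most 7/430 = 1.6%; within cohort 1, 7/250 = 2.8%.

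**2. How long is the recall gap?**

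- Inputs: onset on day 1 to 2 and median duration of 1 to 2 days (Risk/Benefit; local reactions to mRNA-1273); questionnaire at day 28 (calendars).
- Resolution: 1 + 1 = day 2 to 2 + 2 = day 4.
- Gap at day 28: 28 − 4 = 24 to 28 − 2 = 26 days.
- If the 7-day window is read as plus or minus, the visit falls on day 21 to 35, and the gap is 21 − 4 = 17 to 35 − 2 = 33 days.

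**3. How large could the error be? (assumed illustration only)**

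The documents give no recall accuracy, so the bias cannot be computed. To show the scale, assume a true rate of 40% for some reaction and that recall captures between 70% and 90% of true cases, with no false reports.

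- Recorded rate = true rate × capture: 0.40 × 0.70 = 28% to 0.40 × 0.90 = 36%, an undercount of 4 to 12 points.
- Cohort 2, equal true rates and equal capture: spurious difference of 0.
- Cohort 2, equal true rates but capture of 90% against 70%: 36% − 28% = 8 points.
- For comparison, the standard error of a difference at 40% with 50 per arm is √(2 × 0.4 × 0.6 / 50) = 9.8 points.

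The 40% is near the headache (38.9%) and fatigue (38.2%) rates that Risk/Benefit reports for Ad26.COV2.S. The capture rates have no source in the documents, and nothing in them says which arm would recall less.

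**The case against.** The strongest reply is that the timing was a deliberate choice for an exploratory study. The Data and Safety Monitoring Plan explains that closer monitoring was relaxed once the mRNA boosters were authorized. Serious events have other routes: observation, the 24-hour contact, weekly review, the DSMC, and repeated cohort 2 questionnaires aimed at TTS. All of this stands for serious events. It does not supply early data on mild and moderate reactions, and the stated reason concerns the two mRNA boosters, not Ad26.COV2.S as given in cohort 2.

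A second reply is that the time-course figure is narrow. This also stands. It is a median, for local reactions, in the mRNA-1273 trial, and mRNA-1273 is not a study dose in cohorts 2 or 3. No duration is given for systemic reactions, BNT162b2 or Ad26.COV2.S. The 24 to 26 days therefore describe that one case. The day-28 timing itself applies to all cohorts.

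A third reply is that the Statistical analysis section specifies no between-arm safety test, and that the illustrated 8 points is smaller than one standard error. Both are correct. They limit the consequence to descriptive reporting. Cohort 2's second aim still covers side effects of both vaccines, and rates for the two arms will naturally be read together.

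Three stronger readings are tempting, but the documents do not support them:

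- A reader might infer that the run-in checks make side-effect rates by prior vaccine type incomparable. The listed cohort 1 outcome by prior vaccine type is booster efficacy, not safety. Only three patients have the extra checks, and the calendar does not exempt them from the D28 questionnaire.
- A reader might infer that hesitancy about Ad26.COV2.S biases recall within cohort 2. Candidates who prefer not to be randomized are offered cohort 3, so cohort 2 consists of people who accepted either vaccine. The absence of any described blinding is the sounder basis.
- A reader might infer that under-counting, or a spurious arm difference, is established. It is not; both are possibilities of unknown size.

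**Conclusion.** The point holds as a minor one. For all but about 1% to 2% of planned patients, the first scheduled side-effect record is a self-completed questionnaire at about day 28. For the one reaction type whose time course the protocol gives, that is roughly 24 to 26 days after typical resolution (17 to 33 if the visit window runs both ways). The secondary safety outcome is thus open to recall error for mild and moderate reactions. In cohort 2 the error could differ by arm, assuming patients know their vaccine, since no blinding is described.

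The direction and size of the error cannot be derived from the documents; the 4 to 12 point undercount and the 0 to 8 point arm difference are illustrations on assumed recall rates. The serious-event routes and the primary immunogenicity endpoints are untouched. The case for acting is that the error is cheap to reduce, and the run-in already shows that the team can ask about symptoms in the first week.

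**What to change.** Give every patient a side-effect form at the vaccine visit, to be completed at home over the first 7 days and returned at the existing D28 visit. The current questionnaire can be the starting point, but it needs adapting: daily entries, with severity graded on its own scale rather than only against earlier doses.

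Keep the D28 questionnaire for every patient, both for later events and as a common measure. State in the analysis section that early reactions are reported mainly from the 7-day record. Show the D28 recall result and the form return rate alongside it, by arm in cohort 2. Showing the two sources separately, rather than filling missing forms with D28 answers, avoids mixing measurement methods and lets the reader see whether non-return differs by arm.

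The cost is printing, a short instruction at D0 and a little more data entry, with no extra visit, staff or sample. Some forms will not come back; for those patients only the D28 answers remain, which is what the plan has now. The change concerns data collection only and alters neither vaccination nor care.

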Have received an FDA authorized booster dose of mRNA (BNT162b2 or mRNA 1273) vaccine at least 28 days before study enrollment

Exclusion Criteria

Patients who have had a serious adverse reaction to any prior COVID-19 vaccines resulting in emergency room visit or hospitalization, had events related to myocarditis, thrombosis and thrombocytopenia syndrome or anaphylaxis to any prior dose of the COVID-19 vaccines.

Patients who have had a documented COVID-19 infection in the 90 days prior to study enrollment

Outcomes

Primary outcome: Rates of seroconversion for SARS-CoV-2 spike antibody after 4 weeks following an additional booster dose of BNT162b2/AdCov2.S COVID vaccine in patients that had a poor serological response after standard vaccine series (allowing additional booster dose)

Secondary outcomes: Safety of booster dose of BNT162b2 and AdCov2.S vaccines, correlation between malignancy type and prior treatment type and seroconversion, correlation between timing of most recent cancer-directed treatment and seroconversion, correlation between the total number of cancer-directed treatments received and seroconversion, differences between booster efficacy dependent on prior vaccine type (BNT162b2 versus mRNA-1273), T cell responses at baseline and 4 weeks following vaccination, Antigen neutralization assay results at baseline and 4 weeks following vaccination, duration of sustained immunogenicity following vaccination in seropositive patients, correlations with baseline immune status correlates such as lymphocyte subsets/immune globulin levels

Safety monitoring.

Patients who have met all eligibility criteria will then be randomized 1:1 to receive either the BNT162b2 or AdCov2.S and then will be scheduled to receive their study dose at the Montefiore Vaccine Center. Each patient will be observed for a minimum of 15 minutes after their vaccination to monitor for any adverse

effects in the Montefiore Vaccine Center as per the Vaccine Center protocol.

Cohort 3

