On December 16, 2021 the CDC published updated recommendations regarding use of the Ad26.COV2.S (Johnson & Johnson) vaccine (<https://www.cdc.gov/media/releases/2021/s1216-covid-19-vaccines.html>) due to the rare but persistent adverse event thrombosis with thrombocytopenia syndrome (TTS) seen with the Ad26.COV2.S vaccine alone. They expressed a clinical preference for individuals to receive an mRNA COVID-19 vaccine over an Ad26.COV2.S vaccine, however, reaffirmed that receiving any vaccine is better than being unvaccinated. This recommendation, however, did not specify stipulations for our currently immunosuppressed patients with cancer population who have already received three prior mRNA COVID-19 vaccines with minimal or no response. Given our patient population remains at high-risk for severe COVID-19 despite three prior mRNA COVID-19 vaccines, we feel the administration and efficacy evaluation of Ad26.COV2.S (Johnson & Johnson) vaccine as a mix and match strategy for booster vaccination continues to remain warranted as part of our study. In fact, a recent study from South Africa does suggest excellent efficacy of a booster Ad26.COV2.S vaccine corroborating this approach¹⁵.

Some patients, however, remain hesitant to receive an Ad26.COV2.S given its rare but potentially severe adverse event as outlined above. Thereby, for study candidates who prefer not be randomized in cohort 2, participation in cohort 3 will be offered. Cohort 3 will be a prospective, non-randomized cohort to address the question of whether a switch mRNA vaccine approach might be more effective at achieving an increased immune response in poor responders to a prior series of three mRNA vaccinations (mRNA-1273 (Moderna) or BNT162b2 (Pfizer/BioNTech)). Eligible patients will be prospectively followed to receive a BNT162b2 vaccine as a fourth dose evaluating their increase in mean SARS-CoV-2 Spike IgG titers above a pre-established threshold by 4 weeks following vaccination as the primary endpoint with further secondary endpoints regarding safety, neutralization antibody and T cell assays and durability of response with assessments at 3, 6, 12 and 24 months. As it is anticipated that about 60-70% of study candidates will have previously received BNT162b2 and 30-40% mRNA-1273, this cohort will allow an assessment of a switch approach in a non-randomized single arm fashion.

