Severe allergic reactions (including anaphylaxis), thrombosis with thrombocytopenia syndrome (TTS), Guillain-Barré syndrome, and capillary leak syndrome have been reported following administration of the Janssen COVID-19 Vaccine during mass vaccination outside of clinical trials. On December 16, 2021 the CDC published updated recommendations regarding use of the Ad26.COV2.S (Johnson & Johnson) vaccine (<https://www.cdc.gov/media/releases/2021/s1216-covid-19-vaccines.html>) due to the rare but persistent adverse event thrombosis with thrombocytopenia syndrome (TTS) seen with the Ad26.COV2.S vaccine alone. They expressed a clinical preference for individuals to receive an mRNA COVID-19 vaccine over an Ad26.COV2.S vaccine, however, reaffirmed that receiving any vaccine is better than being unvaccinated and no recommendations were outlined with respect to use in immunocompromised patients after previous three dose vaccination series with prior mRNA vaccines.

To reduce the risk of serious adverse effects from the booster vaccine, we will include a safety run-in phase for those that have received prior adenoviral vaccine with close monitoring as described in the methods above.

The primary risks of phlebotomy include local discomfort, occasional bleeding or bruising of the skin at the site of needle puncture, hematoma and, rarely, infection or fainting. To reduce the risk of injury from a fall, each subject will be phlebotomized in a sitting or recumbent position, closely monitored and asked about these symptoms before being allowed to stand up post- phlebotomy.

Another foreseeable risk is that of inadvertent disclosure of HIPAA protected information. As a measure to minimize such risks the collected data will be accessed only by approved individuals, will be collected onto the Excel Data Collection Sheet, and stored on encrypted Montefiore Secure Drive, MonteBox.

Patients may or may not receive personal, direct benefit from taking part in this study. The possible benefits of taking part in this study include developing an immune response to the COVID vaccine, which may help prevent infection and/or severe illness from COVID-19 including death. Participation in this study, however, does not guarantee these direct benefits.

Compensation

Patients will not be offered compensation for participating in our study but might be offered reimbursement for limited travel expenses not exceeding \$100.

Study calendar cohort 1

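### Cohort 2 questionnaires are meant to screen for TTS, but Ad26.COV2.S recipients have no scheduled safety contact between the on-site observation and D28; the trial's early symptom checks and hold rule cover a different group

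*Combined protocol and SAP*

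**What the plan says.** **The run-in.** Methods describes a "run-in phase where 3 patients will receive the vaccine first and followed closely with symptom check at 48 hours and 1 week post-vaccination". It then says what is being tested: "Once safety of booster mRNA vaccine post adenoviral vaccine is established, further enrollment onto the adenoviral vaccine arm will occur". The Data and Safety Monitoring Plan repeats the run-in: "For patients that have received adenoviral vaccine, we plan for a safety run-in when only 3 subjects from the adenoviral vaccine type will be dosed". It attaches the hold rule, under which further patients are dosed "Only if no unexpected or severe side effects (such as adverse events leading to emergency room visit, anaphylaxis, hospitalization or death") are seen. Risk/Benefit gives the same scope: "we will include a safety run-in phase for those that have received prior adenoviral vaccine with close monitoring as described in the methods above". The separate run-in for mRNA-primed patients was closed early, after four had been enrolled.

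**Cohort 2.** Eligible patients have had three mRNA doses. They are randomized 1:1 to BNT162b2 or Ad26.COV2.S, up to 100 in total. Under the cohort 2 Safety monitoring text, "Each patient will be observed for a minimum of 15 minutes after their vaccination to monitor for any adverse" effects. Methods places the next visit at 28 days or later, and the cohort 2 calendar allows a 7-day window. The calendar's safety questionnaire falls at D28, D90, D180, D365 and D730.

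**The named risk.** The cohort 3 rationale and Risk/Benefit both refer to the "rare but persistent adverse event thrombosis with thrombocytopenia syndrome (TTS) seen with the Ad26.COV2.S vaccine alone". Risk/Benefit also lists Guillain-Barré syndrome and capillary leak syndrome for this vaccine. The Data and Safety Monitoring Plan says that cohort 2 patients complete safety questionnaires at each follow-up visit in order to screen for TTS.

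**The concern.** The protocol has a procedure for early safety data: scheduled symptom checks at 48 hours and 1 week, with a stated condition for going on. It applies this to three cohort 1 patients, none of whom receives Ad26.COV2.S as a study dose. The patients who do receive it, all in cohort 2, fall outside the procedure, although the protocol singles out that vaccine for TTS and says that it intends to screen them.

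The stated justification does not reach them either. The Data and Safety Monitoring Plan relaxed its earlier monitoring because booster dosing with the two mRNA vaccines had been authorized. The authorization it cites does not cover Ad26.COV2.S, and Methods describes it as being for a third dose, whereas cohort 2 receives a fourth.

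At stake is how soon a serious event in a cohort 2 patient would become known to the study team, and what the protocol then says about further dosing. An event in the first four weeks reaches the team only if the patient or a treating clinician reports it, or when the D28 questionnaire is completed.

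**Working it through.** No stated figure is in dispute. The check sets the sections side by side, with a short calculation to bound what early checks could show.

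**1. Whom the run-in covers.** In the Data and Safety Monitoring Plan, the words about subjects of the adenoviral vaccine type could be taken to include people who receive Ad26.COV2.S in cohort 2. Two other sections rule that out: Methods names an mRNA booster after adenoviral vaccine, and Risk/Benefit limits the run-in to prior adenoviral recipients. Cohort 2 requires three prior mRNA doses.

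**2. Scheduled safety contact after dosing.**

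| Group | Study vaccine | On site | Next scheduled contact | Stated hold rule | Questionnaires |
|---|---|---|---|---|---|
| Cohort 1, prior Ad26.COV2.S, first 3 | mRNA | Extended observation | 48 hours, 1 week | Yes | D28 |
| Cohort 1, prior mRNA | mRNA | At least 15 min | D28 | No | D28 |
| Cohort 2 | BNT162b2 or Ad26.COV2.S | At least 15 min | D28 | No | D28, D90, D180, D365, D730 |
| Cohort 3 | BNT162b2 | At least 15 min | D28 | No | D28, D90, D180, D365, D730 |

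With a visit at 28 days or later and a 7-day window, the first cohort 2 questionnaire falls at D28 to D35. Until then, cohort 2 has the same schedule as cohort 3, which does not give Ad26.COV2.S.

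**3. Number of patients.** Up to 100 patients at 1:1 gives 100 / 2 = about 50 on Ad26.COV2.S. The run-in covers 3 patients, none given it as a study dose.

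**4. What else applies.** The Data and Safety Monitoring Plan provides weekly team meetings during vaccination and for at least 4 weeks afterwards, alerts to the IRB and DSMC for serious adverse events, and DSMC monitoring. Methods gives every enrolled patient a 24-hour contact. The meetings review whatever data are available, and none is scheduled from a cohort 2 patient between D0 and D28. The contact line depends on the patient calling. Neither section states when cohort 2 dosing would pause.

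**5. What small numbers can show.** With zero events in n patients, the one-sided 95% upper bound on the event rate is 1 − 0.05^(1/n):
- n = 3: 1 − 0.05^(1/3) = 63%
- n = 50: 1 − 0.05^(1/50) = 5.8%

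The chance of at least one event is 1 − (1 − p)^n. The documents give no TTS rate, so p is assumed over a range:

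| Assumed p | n = 3 | n = 50 |
|---|---|---|
| 0.1% | 0.3% | 4.9% |
| 1% | 3.0% | 39% |
| 5% | 14% | 92% |

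Neither three patients nor the whole arm could reliably reveal a rare event. Early contacts would help by finding an event sooner in the patient who has it. They would not establish that the vaccine is safe.

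**The case against.** The strongest reply is that cohort 2 is monitored and that the sponsor dealt with TTS openly. There are weekly reviews, IRB and DSMC alerts, DSMC monitoring and a 24-hour contact. Patients with prior TTS are excluded, cohort 3 is offered to those who decline randomization, and questionnaires run to D730. The sections on the run-in agree with one another, so not extending it could be called a design preference. A three-patient gate would also do almost nothing against a rare event.

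Much of this stands. It rules out several stronger readings that a reader might reach:

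- *Cohort 2 has the weakest safety gate in the trial.* It does not. Cohort 3 has the same schedule, and mRNA-primed cohort 1 patients also have no scheduled contact before D28 and have fewer questionnaires.
- *Risk/Benefit misstates the run-in.* It does not; "we will include a safety run-in phase for those that have received prior adenoviral vaccine with close monitoring" is accurate. Its place shortly after the TTS paragraph may mislead, but the sentence claims no coverage of cohort 2.
- *No event could stop cohort 2 dosing.* The documents do not show this. Serious events are handled under institutional protocols that are not reproduced. What can be said is that this protocol states no hold condition for cohort 2.
- *Many patients would be dosed before the first questionnaire.* The documents give no accrual rate, so no such count can be supported.

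What the reply does not answer is the mismatch between the stated purpose of the cohort 2 questionnaires and a schedule with nothing in the first four weeks. Reviewing available data does not generate data, and an exclusion criterion is not monitoring.

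**Conclusion.** The concern holds in a limited form. Up to about 50 patients receive Ad26.COV2.S with no scheduled safety contact from the end of on-site observation to D28 (D35 at the end of the window), and with no hold condition stated for them in the protocol. Their monitoring before D28 is no stronger than in a cohort that does not receive that vaccine, despite the stated aim of screening for TTS and a justification that rests on mRNA boosters.

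This takes the run-in's scope from Methods and Risk/Benefit, takes the cohort 2 calendar as complete, and reads the weekly review and 24-hour contact generously as covering all cohorts. It does not depend on an accrual rate or a TTS rate. It is a gap in the timing of safety ascertainment and in the stated scope of the hold paragraph, not evidence that cohort 2 is unmonitored.

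**What to change.** Reconcile the cohort 2 Safety monitoring text, Methods, the Data and Safety Monitoring Plan, Risk/Benefit and the cohort 2 calendar, so that the aim of screening cohort 2 for TTS matches the schedule.

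- **Early data collection.** The symptom contacts that the protocol already uses at 48 hours and 1 week, applied to both cohort 2 arms and entered in the calendar, would do this. Collecting them alike in both arms keeps the safety comparison balanced. The results would go to the existing weekly review and the DSMC.
- **Scope of the hold paragraph.** State expressly whether it covers cohort 2 patients who receive Ad26.COV2.S. Whether a hold criterion applies, and which one, is for the sponsor and the DSMC to decide; none is proposed here.

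The cost is a protocol amendment and two short contacts per cohort 2 patient by the existing team: 2 × 100 = 200 contacts at most. No extra patients are needed.
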